5.2.3 Safety Evaluable Population

The safety population will consist of all subjects who received at least one dose of the study medication. All safety endpoints will be summarized for the safety population. Analysis will be done according to the actual treatment subjects received.

5.2.4 Per-Protocol (PP) Population

The PP population will be a subset of the ITT population that only includes subjects who have complete baseline and Week 12 assessments without any protocol deviation(s) which would interfere with the assessment of efficacy.

Such protocol deviations are departures from the approved protocol relating to the conduct of the study which may affect the rights, safety, and/or wellbeing of study participants or the study outcomes or data quality. A listing of study subjects with protocol deviations which would preclude inclusion in the PP population will be provided by the Sponsor prior to database lock.

The PP population is a supportive analysis population for the primary and secondary efficacy endpoints, and will be used in sensitivity analyses as needed. Analysis will be done according to the treatment subjects were randomized to.

5.3 Subject Disposition

All subjects who signed the informed consent will be accounted for in Subject Disposition. The following disposition information will be summarized by the number and percentages of subjects:

- Subjects who signed the informed consent, and who comprise the ITT, mITT/Evaluable, Safety, and PP populations
- Subjects who complete the study or withdraw prematurely along with the reason for discontinuation

A listing of screen failure subjects, including age, sex, race, ethnicity, education, and the inclusion/exclusion criteria not met, will be provided.

A listing of subjects excluded from each of the analysis populations, including population flags (Safety/mITT/Evaluable) and the reason for exclusion, will be provided.

5.4 Demographics and other Baseline Characteristics

5.4.1 Demographics

Sex, age (in years), race, ethnicity, education, and baseline body mass index (BMI) (kg/m^2) will be summarized by treatment group for the ITT and mITT/Evaluable populations. BMI (kg/m^2) will be calculated as: $10,000 \times \text{weight (kg)} / \text{the square of height (cm)}$. If height is collected in inches, it will be converted to cm by dividing the value by 2.54. If weight is collected in pounds, it will be converted to kg by dividing the value by 2.205.

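### SAP section 5.4.1 divides inches by 2.54 to obtain centimetres instead of multiplying, so a BMI derived from a height in inches is 41.6 times too large

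*SAP*

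**What the plan says.** Section 5.4.1 (Demographics) lists BMI among the variables to be tabulated: "baseline body mass index (BMI) (kg/m^2) will be summarized by treatment group for the ITT and mITT/Evaluable populations". It defines BMI as 10,000 times weight in kilograms divided by the square of height in centimetres, and then gives two conversions for data recorded in other units.

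- Height: "If height is collected in inches, it will be converted to cm by dividing the value by 2.54".
- Weight: "If weight is collected in pounds, it will be converted to kg by dividing the value by 2.205".

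Section 5.1 (General Considerations) says how continuous variables are summarised: by mean, standard deviation, median and range. No other section gives a different height conversion.

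**The concern.** The two conversions are worded in parallel, but only one is right. A pound is less than a kilogram, so dividing pounds by 2.205 is correct. An inch is longer than a centimetre, so inches must be multiplied by 2.54. The height rule is therefore the inverse of the true conversion.

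The sentence is a derivation instruction, and its result goes straight into the BMI formula, where height is squared, so the error is squared as well. A programmer who follows the SAP literally would produce wrong BMI values for every subject whose height was recorded in inches. A second programmer working independently from the same text would reproduce them, so agreement between the two would not expose the fault. What is at stake is the BMI row of the demographics tables for two analysis populations.

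**Working it through.** The SAP states no BMI value, so there is no figure of its own to reproduce. The check is direct arithmetic on the rules in section 5.4.1.

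**Inputs from the SAP**

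- BMI = 10,000 × kg / cm²
- kg = lb / 2.205
- cm = in / 2.54, as written

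The correct height conversion is cm = in × 2.54.

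**The parts that are right**

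- BMI formula, metric check: 80 kg and 175 cm give 10,000 × 80 / 175² = 26.12, the same as 80 / 1.75² = 26.12.
- Weight rule: 1 / 2.205 = 0.4535 kg per pound, against 0.4536.

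**Size of the error**

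- Converted height, correct over as written: (in × 2.54) / (in / 2.54) = 2.54² = 6.4516.
- BMI, as written over correct: 6.4516² = 2.54⁴ = 41.623. Height and weight cancel, so the factor is the same for every subject.

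**Illustrative subjects** (heights and weights are assumed)

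| Height, weight | BMI, correct | BMI, as written |
|---|---|---|
| 60 in, 120 lb | 23.4 | 975.3 |
| 65 in, 150 lb | 25.0 | 1,038.8 |
| 70 in, 180 lb | 25.8 | 1,074.8 |
| 72 in, 200 lb | 27.1 | 1,128.8 |

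The third row in full: 180 / 2.205 = 81.63 kg. Correct height is 70 × 2.54 = 177.8 cm, so BMI = 10,000 × 81.63 / 177.8² = 25.8. As written, height is 70 / 2.54 = 27.56 cm, so BMI = 10,000 × 81.63 / 27.56² = 1,074.8 (calculated without rounding the intermediate values).

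**Effect on a summary table**

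This needs three inputs that the SAP does not give. Assume a true mean BMI of 26, a true SD of 4, and a proportion p of heights recorded in inches. With k = 41.623:

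- mean = (1 − p) × 26 + p × 26 × k
- SD = √[(1 − p)(26² + 4²) + p × k² × (26² + 4²) − mean²]
- median = the 50% point of the mixture of N(26, 4) and N(26k, 4k), where the second argument is the SD

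| p | Mean | SD | Median |
|---|---|---|---|
| 0% | 26 | 4 | 26 |
| 5% | 78.8 | 233.2 | 26.3 |
| 10% | 131.6 | 321.2 | 26.6 |
| 20% | 237.2 | 429.0 | 27.3 |

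For p = 5%: mean = 0.95 × 26 + 0.05 × 26 × 41.623 = 78.8. Over 5% to 20%, the mean and SD become meaningless and the maximum is near or above 1,000, while the median moves by little more than one unit. The stability of the median should not be read beyond that range: at 45% in inches it would be near 31 (0.5 / 0.55 = 0.909, z ≈ 1.34, 26 + 4 × 1.34 ≈ 31.4).

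**The case against.** The case on the other side concerns weight, not fact.

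- **The rule may never run.** It is conditional, and the SAP does not show that any height is recorded in inches. This stands as a limit on the consequence. But the SAP provides for that case, and section 4.1 describes about 30 sites globally, so the rule should be right when it is needed.
- **BMI is only descriptive.** This stands in full. BMI is not an endpoint, not the stratification factor (sex, section 4.5.1), not a term in the MMRM (section 5.7.1) or the sensitivity ANCOVA (section 5.7.1.1), and not a condition for any analysis population (section 5.2).
- **The error would reveal itself.** A BMI near 1,000 would probably be noticed once the range is printed. That makes a wrong published table less likely; it does not make the written rule right. A programmer who silently corrected it would be departing from the SAP, and section 5.1 calls for departures from the planned analyses to be noted in the CSR.
- **The effect on real output is unknown.** This also stands. The SAP establishes a wrong instruction, not a wrong reported value, because the program itself is not shown.
- **The table-level figures rest on assumptions.** They do. The factor of 41.6 does not, and it is enough to establish the point.

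**Conclusion.** The height conversion is wrong as written. Any BMI derived from a height in inches under this rule is too large by exactly 2.54⁴ = 41.6; this follows from the definition of the inch and the SAP's own formula and needs no assumption. How far the demographics tables would be affected depends on the share of heights recorded in inches, which the SAP does not state. There is no effect if all heights are in centimetres, and severe distortion of the mean, SD and maximum at an assumed 5% to 20%. The consequence is confined to the descriptive BMI summaries in the ITT and mITT/Evaluable populations. The primary analysis and the other efficacy analyses are untouched. It is a small point, but a certain one, and it should be corrected.

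**What to change.** In the height sentence of section 5.4.1, replace *dividing* with *multiplying*, so that inches are multiplied by 2.54 to give centimetres. Leave the weight conversion and the BMI formula unchanged. Check that the program deriving BMI multiplies, and if any demographics tables have already been produced, check the BMI minimum and maximum for values that could come from the inverted rule.

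The cost is one word in the SAP and one check of the program. No efficacy analysis, sample size or analysis population changes.

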5.4.2 Baseline Characteristics

Baseline characteristics will be summarized by treatment group for the ITT and mITT/Evaluable populations.

Baseline characteristics to be summarized are:

- Disease Duration
- Modified Hoehn and Yahr
- MDS-UPDRS Parts 3 in the off-medication state

5.4.3 Medical History

The number and percentage of subjects with any medical history will be summarized for the ITT population by treatment group, SOC, and PT using the MedDRA dictionary.

The following will be provided in listings only:

- Family history in biological parents, siblings, and offspring of PD, Alzheimer's disease (AD), or other dementias or neurological disorders
- Cause of parental death (if not living)
- History of tobacco and substance use
- Social history and exercise/activity level

5.5 Protocol Deviations

Protocol deviations will be summarized by deviation category, major vs minor and treatment group for the ITT population, with flags for the mITT/Evaluable, Safety, and PP populations.

5.6 Methods for Handling Missing Data

In order to minimize missing data, every effort will be made to obtain required data for all randomized subjects at each scheduled evaluation. However, in the event that more than 5% of data are missing, imputation methods will be used for analysis of the primary endpoint only. The imputation will be carried out in SAS version 9.4 or later using PROC MI.

5.7 Efficacy Analyses

Efficacy analyses will evaluate the effects of AKST4290 on motor function in the off-medication state, as well as the potential effects on clinical function and activities of daily living. Efficacy endpoints will be evaluated using the mITT/Evaluable and PP populations.

5.7.1 Primary Efficacy Endpoint

The primary endpoint is change from baseline at Week 12 (Day 84) in the off-medication motor function as measured by the MDS-UPDRS Part 3. The main analysis for the primary efficacy variable will be analyzed using mITT subjects.

The MDS-UPDRS (Fahn, 1987; Goetz, 2008) was developed to incorporate elements from existing scales to provide a comprehensive but efficient and flexible means to monitor PD-related disability and impairment. The MDS-UPDRS has four components (Part 1, Mentation, Behavior, and Mood; Part 2, Activities of Daily Living; Part 3, Motor; Part 4, Complications). The rating for each item is from 0 (normal) to 4 (severe). The score for each Part is obtained from the sum of the corresponding item scores.

The null and alternative hypotheses for the primary endpoint are:

$$H_0: \mu_C = \mu_T \text{ vs. } H_A: \mu_C \neq \mu_T.$$

The null hypothesis states that there is no difference in mean change (μ) from baseline motor function during the practically defined off-medication state at Week 12 - as measured by the MDS-UPDRS Part 3 - between the control (C) and treated (T) groups. The alternative hypothesis states that there is a difference in mean change from baseline motor function during the practically defined off-medication state at Week 12 between the control and treated groups.

The MDS-UPDRS Part 3 is administered in the off-medication state at Baseline (Study Day 1) and Weeks 4 (Day 28), 12 (Day 84), and 14 (Day 98). The sum of corresponding items for section 3 will be summarized descriptively at each scheduled visit. Additionally, the number and percentage of subjects with dyskinesia present during the evaluation, and whether that dyskinesia interfered with ratings, will be presented.

A mixed-effect model for repeated measures (MMRM) will be employed to analyze the change from baseline scores at each visit over time up to Week 12. The model will include the fixed effects of treatment (stratified, by sex), baseline of the endpoint, visit, and treatment by visit interaction. An unstructured covariance structure will be used to model the within subject error. Least-square (LS) means, standard error (SE), and 95% CI of the LS mean will be provided for each treatment arm at each visit. The unadjusted mean change from baseline, and the difference in LS means between treatment arms and 95% CI of the difference will also be calculated. P-value for testing whether the difference is equal to zero will be provided. The p-value at Week 12 will be compared against the alpha significance level of 0.1.

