4.3 Statistical Hypothesis

[figure not shown]
The null and alternative hypotheses for primary endpoint analysis are:

$$H_0: \mu_C = \mu_T \text{ vs. } H_A: \mu_C \neq \mu_T.$$

The null hypothesis is that there is no difference in mean change (μ) from baseline motor function during the practically defined off-medication state at Week 12 - as measured by the MDS-UPDRS Part 3 - between the control (C) and treated (T) groups. The alternative hypothesis is that there is a difference in mean change from baseline motor function during the practically defined off-medication state at Week 12 between the control and treated groups. P-values for testing whether the differences are equal to zero will be provided. P-values will be compared against an alpha significance level of 0.1.

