5.1 General Considerations

This section presents the statistical approaches that are anticipated for the analysis of the study data. These approaches may at times require modifications due to unanticipated features of the data. Deviations from analyses summarized in this document will be noted in the clinical study report (CSR).

All statistical analyses will be performed using SAS® Version 9.4 or higher, unless otherwise noted. All summary statistics will be descriptive unless noted otherwise. Descriptive summaries will include mean, standard deviation (STD), median, and range for continuous variables and counts, and percentages for categorical variables. Two-sided 95% confidence intervals (CIs) will be provided for the means and percentages as needed. For key outcome measures, the difference between the treatment arms and the 95% CI of the difference will be computed, as necessary. Presentations will be by treatment group, unless otherwise noted.

In general, all summary tables will be supported by a relevant subject data listing including all subjects who are randomized. The listings will include all data collected, and will be sorted by subject ID, and actual visit date, as applicable, unless otherwise noted.

Concomitant medications will be coded by the World Health Organization (WHO) Drug Dictionary and adverse events and medical history will be coded using the MedDRA. The dictionary versions will be documented in the Data Management Plan for the study.

Study day 1 is the first day of study treatment. Study day is the day relative to the study day 1. Baseline is the last non-missing valid value prior to study treatment.

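### Does a primary test at two-sided alpha 0.10, reported with only a 95% confidence interval, leave the trial's conclusion in doubt?

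*SAP*

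**What the plan says.** Section 4.3 sets equality of the two mean changes against inequality ("The alternative hypothesis is that there is a difference in mean change from baseline motor function") and gives the threshold: "P-values will be compared against an alpha significance level of 0.1". Section 5.7.1 repeats the hypotheses. For the repeated-measures model it says "P-value for testing whether the difference is equal to zero will be provided", followed by the threshold for Week 12: "The p-value at Week 12 will be compared against the alpha significance level of 0.1".

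The intervals are set separately. In section 5.7.1, "the difference in LS means between treatment arms and 95% CI of the difference will also be calculated". The general rules in section 5.1 are the same: "Two-sided 95% confidence intervals (CIs) will be provided for the means and percentages as needed", and for key outcomes "the difference between the treatment arms and the 95% CI of the difference will be computed", there qualified as being done where necessary. The SAP has no 90% interval. It does not say in words that the 95% interval is descriptive.

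**The concern.** A two-sided test at level 0.10 corresponds to a 90% interval, and a 95% interval corresponds to a test at 0.05. With the threshold at 0.10 and the interval at 95%, a band of results exists in which the table shows a significant p-value next to an interval that covers zero. A threshold of 0.10 makes a difference, compared with 0.05, only in that band.

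If the interval were a second criterion, the plan would hold two rules of different strictness for its main comparison. The choice between them could then be made after the results were known.

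**Working it through.** **Inputs.** Alpha is 0.10 (sections 4.3 and 5.7.1). The test is two-sided, read from the not-equal alternative. The null value is zero and the interval level is 95% (sections 5.1 and 5.7.1). About 120 subjects are to be randomized 1:1 for about 108 evaluable (section 4.4), or 54 per arm if split equally. Section 4.4 gives no effect size, standard deviation or power, so the power levels below are assumptions.

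**1. The two cut-offs.**
- The test rejects when |estimate/SE| > z(0.95) = 1.645.
- The 95% interval excludes zero when |estimate/SE| > z(0.975) = 1.960.
- With about 105 degrees of freedom the t values are 1.659 and 1.983.
- The 95% interval is 1.960/1.645 = 1.19 times as wide as the 90% interval.

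**2. An example inside the band, p = 0.07.** Here z = 1.812.
- 95% interval in SE units: 1.812 ± 1.960 = −0.148 to 3.772, which includes zero.
- 90% interval: 1.812 ± 1.645 = 0.167 to 3.457, which excludes zero.

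**3. Where the band lies.** In a simple two-mean approximation with 54 per arm, SE = SD × √(2/54) = 0.192 SD. The band is 1.645 × 0.192 to 1.960 × 0.192, or an observed difference of about 0.32 to 0.38 SD.

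**4. How often it occurs.** With no effect: 0.10 − 0.05 = 0.05, which is half of all false positives. With an effect, set the drift to 1.645 + z(power) and subtract the rejection probability at 0.05 from that at 0.10:

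| Assumed power at 0.10 | Drift | P(reject at 0.10) | P(reject at 0.05) | P(in the band) |
|---|---|---|---|---|
| 50% | 1.645 | 0.501 | 0.376 | 0.124 |
| 70% | 2.169 | 0.700 | 0.583 | 0.117 |
| 80% | 2.486 | 0.800 | 0.701 | 0.099 |
| 90% | 2.926 | 0.900 | 0.833 | 0.067 |

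**5. What a 90% interval would add.** The estimate is the midpoint of the 95% interval, and the 90% half-width is the 95% half-width times 1.645/1.960 = 0.839 (1.659/1.983 = 0.837 at 105 degrees of freedom). In the example the midpoint is (−0.148 + 3.772)/2 = 1.812 and the half-width is 1.960 × 0.839 = 1.645. This returns 0.167 to 3.457, the interval in step 2. The planned output already contains the information.

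**6. Which rule decides.** Sections 4.3 and 5.7.1 both compare the p-value with 0.1. Neither they nor section 5.1 compares an interval with zero to reach a conclusion. In section 5.7.1 the interval is an additional calculation, and in section 5.1 it is a general reporting convention.

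**The case for a change.** The best case for a change is that it is cheap and falls where it matters. It would take one more interval in the primary table, or one sentence saying that the 95% interval is descriptive. The results affected are those for which alpha was set at 0.10 instead of 0.05. The sensitivity analyses in section 5.7.1.1 are meant to check robustness but have no numerical criterion, so a reader might judge them by p < 0.10 or by whether the 95% interval excludes zero. Reading alpha as one-sided would not remove the mismatch, because the matching two-sided interval would then be 80%.

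The arithmetic stands, and so does the point that matching the interval to the test is tidier. The stronger consequences do not follow. A p-value of 0.07 and a 95% interval that covers zero come from the same estimate and standard error, and they do not contradict each other. They conflict only if the interval is read as a second test, which the SAP does not do. The roughly 70% chance that the 95% interval excludes zero, at an assumed 80% power, measures success against a criterion the trial does not use, so it is not a loss of power. The sensitivity analyses support the primary result and do not replace its rule. The secondary analyses in section 5.7.2 plan 95% intervals without an alpha threshold, so one interval level throughout the report is a reasonable convention.

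**Conclusion.** No change to the plan follows. The primary test is two-sided at 0.10, its type I error is 0.10 as intended, and the rule that decides is fixed before the data are seen. The 95% interval has its stated coverage. The discordant band, 0.05 < p < 0.10, would be met in 5% of trials with no effect and in about 7% to 12% of trials over assumed powers of 90% down to 50%. Even then the estimate, standard error, p-value and conclusion would be the same with or without a 90% interval.

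This rests on two readings: that the not-equal alternative makes the 0.10 two-sided, and that an interval given no role in the decision is descriptive. If the result falls in the band, the study report can show the 90% interval beside the p-value without any amendment to the SAP.

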5.7.1.1 Sensitivity Analyses

The main analysis of the primary endpoint using the above MMRM will use all available data. To check the robustness of the results, the following sensitivity analyses will be performed:

FM DM015.1
Statistical Analysis Plan
AKST4290-211

Rev B
Page 18 of 30

- Analysis of covariance (ANCOVA) model on the observed change from baseline value at Week 12. The model includes treatment as the fixed effect and baseline of the endpoint as a covariate.
- The same MMRM model on data from the PP subjects.
- The same MMRM model on data from the ITT subjects.
- Depending on the status of missing data among the mITT population, multiple imputations may be employed to handle missing data and apply the MMRM on the imputed datasets. See Methods for Handling Missing Data section (section 5.6) for details on imputation methods.

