4.5.1 Randomization

A randomization list, permuted blocks and stratified by sex (Male and Female) was generated by an outside vendor and is outside the scope of this SAP.

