5.7.2.3 Schwab and England Activities of Daily Living Scale

The SE-ADL evaluates patients' perceptions of global functional capacity and dependence (Schwab, 1968). Scoring is expressed in terms of percentage, in 10 steps from 100 to 0 (100%, normal status; 0%, bedridden with impaired vegetative functions), so that the lower the score, the worse the functional status.

Scores are collected at Baseline, and Weeks 2, 4, 8, 12, and 14. Scores will be summarized descriptively at each scheduled time point (i.e. n, %) by treatment group. A Generalized Estimating Equations (GEE) for alternating logistic regression (ALR) with an exchangeable working correlation structure will be employed to analyze change from baseline. The model will include the fixed effects of treatment, baseline of the endpoint, visit, and treatment by visit interaction. The common odds ratio and 95% CI for odds of higher versus lower SE-ADL scores between treatment groups will be presented. Mean scores at each timepoint, and change from baseline, will also be presented.

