5.7.3.2 Wearable Sensor Device

A wearable sensor device allowing for the continuous measurement of health-related symptoms, including the motor and nonmotor features of bradykinesia, tremor, general activity, and sleep, will be provided to applicable subjects at Screening, Week 4, and Week 8. Data will then be collected over a 6-day period and returned at the following visit (i.e. Baseline, Week 8, and End of Treatment). Bradykinesia, tremor, general activity, and sleep parameters will be summarized descriptively at each applicable timepoint.

To evaluate change from baseline, the same MMRM model used to evaluate the primary endpoint will be employed to produce LS means, SE, and 95% CIs of the LS means for each treatment arm at each scheduled

visit. The unadjusted mean change from baseline, and the difference in LS means between treatment arms and 95% CI of the difference will also be calculated.

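### Sex stratifies the randomization but is left out of the sensitivity ANCOVA and is not a clear term in the primary MMRM

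*SAP*

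**What the plan says.** SAP 4.5.1 describes the allocation: "A randomization list, permuted blocks and stratified by sex (Male and Female) was generated by an outside vendor". No other stratification factor is given.

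SAP 5.7.1 specifies the primary MMRM: "The model will include the fixed effects of treatment (stratified, by sex), baseline of the endpoint, visit, and treatment by visit interaction". Its outputs are arm-level: "Least-square (LS) means, standard error (SE), and 95% CI of the LS mean will be provided for each treatment arm at each visit". There is one test: "The p-value at Week 12 will be compared against the alpha significance level of 0.1".

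SAP 5.7.1.1 adds an ANCOVA of the observed Week 12 change as a sensitivity analysis: "The model includes treatment as the fixed effect and baseline of the endpoint as a covariate". Sex is not among its terms.

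The SE-ADL model in SAP 5.7.2.3 has nearly the same list of effects as the MMRM, but without the parenthesis on sex: "The model will include the fixed effects of treatment, baseline of the endpoint, visit, and treatment by visit interaction".

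The primary MMRM is reused for the PP and ITT sensitivity analyses (5.7.1.1), MDS-UPDRS Parts 1-4 (5.7.2.1), CISI-PD (5.7.2.4), PDQ-39 (5.7.2.5), the 10-meter walk (5.7.2.7) and the wearable device (5.7.3.2), the last in these words: "To evaluate change from baseline, the same MMRM model used to evaluate the primary endpoint will be employed".

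**The concern.** An analysis should normally adjust for the factor used to stratify the randomization. Stratified blocks make the arms nearly equal on sex, so the treatment difference does not carry variation between the sexes. A model without sex still counts that variation as residual error, so its standard error overstates the true uncertainty whenever sex predicts the outcome.

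The two models raise different problems. In the ANCOVA, sex is plainly absent. In the MMRM, the parenthesis is not a codable term. A programmer could enter a sex main effect, fit treatment effects within each sex and combine them, or take the words as a note on the randomization and enter nothing. These choices give different standard errors for the one p-value that decides the trial, and the choice should not be open after unblinding.

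If the MMRM adjusts for sex and the ANCOVA does not, the two also differ in covariates as well as in their use of repeated measures. A discrepancy between them could then not be put down to one cause, which weakens the ANCOVA as a robustness check.

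**Working it through.** The SAP states no SD, effect size, power or sex effect, so there is no figure of its own to reproduce.

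**Inputs from the SAP**
- Two-sided test at 0.10 (4.3, 5.7.1).
- 1:1 allocation, about 120 randomized and about 108 evaluable (4.4).

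**Assumptions, not in the SAP**
- Within-sex residual SD of 9, varied from 7 to 12.
- Share of one sex f = 0.40, varied from 0.35 to 0.50.
- Sex difference g in 12-week change, after adjustment for baseline, of 0 to 5 points.
- Power of 80% when the model includes sex, so the true effect is 1.645 + 0.842 = about 2.486 standard errors.

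**1. Sex left out**

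- SE ratio R = sqrt(1 + f(1 − f)g²/SD²)
- Real size = 2 × P(Z > 1.645 × R)
- Power = P(Z > 1.645 × R − 2.486)

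Example for g = 3: f(1 − f) = 0.24, and 0.24 × 9/81 = 0.0267, so R = sqrt(1.0267) = 1.0132.

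| g (points) | R | SE too large by | Real size of 0.10 test | Power |
|---|---|---|---|---|
| 0 | 1.0000 | 0% | 0.1000 | 80.0% |
| 1 | 1.0015 | 0.15% | 0.0995 | – |
| 2 | 1.0059 | 0.6% | 0.0980 | – |
| 3 | 1.0132 | 1.3% | 0.0956 | 79.4% |
| 5 | 1.0364 | 3.6% | 0.0883 | 78.3% |

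Range at SD 9:
- g = 3 gives R = 1.0126 (f = 0.35) to 1.0138 (f = 0.50).
- g = 5 gives R = 1.0345 (f = 0.35) to 1.0379 (f = 0.50).

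Extremes over SD 7 to 12 for g of 3 to 5:
- 1.0071 (SD 12, g = 3, f = 0.35).
- 1.0619 (SD 7, g = 5, f = 0.50).

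**2. Simulation under the null**

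There were 10,000 trials per case: 120 randomized in blocks of 4 within sex, 108 analysed, f = 0.40, SD 9, Week 4 to Week 12 correlation 0.6, the same sex effect at both visits, unstructured covariance. The Monte Carlo error of each size is about 0.003.

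| | g = 0 | g = 3 | g = 5 |
|---|---|---|---|
| MMRM size, without / with sex | 0.100 / 0.102 | 0.094 / 0.098 | 0.087 / 0.097 |
| MMRM mean SE ratio | 1.001 | 1.014 | 1.038 |
| SD of the change in estimate (points) | 0.05 | 0.11 | 0.17 |
| 0.10 verdict differs | 0.5% | 1.2% | 1.6% |
| ANCOVA size, without / with sex | 0.100 / 0.101 | 0.093 / 0.096 | 0.086 / 0.096 |
| ANCOVA mean SE ratio | 1.000 | 1.013 | 1.037 |

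The SE of the treatment difference is about 9 × sqrt(4/108) = 1.73 points, so the estimate itself hardly moves.

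**3. MMRM coded as treatment by sex, sexes weighted equally**

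- SE ratio = 1/(2 × sqrt(f(1 − f)))
- Power = P(Z > 1.645 − 2.486/ratio)

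| f | SE ratio | Power |
|---|---|---|
| 0.50 | 1.0000 | 80.0% |
| 0.40 | 1.0206 | 78.6% |
| 0.35 | 1.0483 | 76.6% |

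**The case against.** The strongest reply is that the MMRM wording is clear enough. Sex stands inside the list of fixed effects, treatment by visit is the only interaction named, and SAP 4.3 and 5.7.1 want one overall contrast and one p-value. A sex main effect is the natural reading, and the treatment-by-sex case, which shows the largest power loss above, is the less natural one. That is fair. For the MMRM the point is close to a clarification of wording.

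Second, the ANCOVA is supportive, the 0.10 threshold is attached to the MMRM, and an unbiased, slightly conservative check is defensible. That is also true. But the SAP gives no reason to leave out the factor it randomizes by.

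Third, the size depends on assumptions. Nothing in the SAP indicates that sex predicts 12-week change, and 5 points is more than half the assumed SD. With a difference of 0 to 2 points the cost is at most 0.6% in SE. Some verdicts differ (0.5%) even with no sex effect, so the excess at 3 to 5 points is about 1 trial in 100. This limits the importance of the point but does not remove it.

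Fourth, the reach is less weighty than the list of analyses suggests. The secondary MMRMs have no stated significance threshold, and SAP 5.7.3 rules out treatment comparisons for exploratory endpoints although 5.7.3.2 specifies one.

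**Conclusion.** The concern holds. The sensitivity ANCOVA omits the only stated stratification factor, and the primary MMRM does not say how sex enters.

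The consequence is small and conservative: no bias, no inflation of type I error, and no cost if sex is not prognostic. The SE excess from omitting sex runs from 0% to 3.6% in the base case. It is 0.7% to 6.2% for sex differences of 3 to 5 points across the assumed SDs and sex shares. All of these sizes rest on assumptions outside the SAP.

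The change is worth making because the primary p-value should come from one fully specified model, its ANCOVA check should use the same adjustment, and the cost is negligible. It is a recommended improvement, not an error that threatens the trial's conclusion.

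**What to change.** - **SAP 5.7.1:** list the MMRM fixed effects as treatment, sex (main effect), baseline, visit and treatment by visit, and state that the test is one overall treatment contrast at Week 12. This carries to every analysis that reuses the model.
- **SAP 5.7.1.1:** add sex as a fixed effect in the sensitivity ANCOVA.
- **Other secondary models** (the SE-ADL model and the ANCOVAs for MoCA, S-STS and the Hauser diary): adding sex is optional, for consistency.

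The cost is SAP wording only. With 108 subjects the ANCOVA goes from 108 − 3 = 105 to 104 degrees of freedom, and the two-sided 0.10 critical t moves from 1.6595 to 1.6596. The design and data collection do not change.
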